5.1.3 Study Plan

See Table of Study Procedures and [Section 5.1.4](#) Visit Procedures for the plan of activities for the study period. [Figure 5.1](#) shows an overview of the study design. [Figure 5.2](#) and [Figure 5.3](#) provide overviews of the study plan and the timeframes for Cohorts 1 and 3, and Cohorts 2 and 4, respectively.

Figure 5.1: Study Design

[figure not shown]

Figure 5.2: Study Plan and Timeframe for Cohorts 1 and 3

[figure not shown]

Figure 5.3: Study Plan and Timeframe for Cohorts 2 and 4

[figure not shown]

Table 5-1: Schedule of blood sample collection (volume in mL) – Cohorts 1 and 3

Visit Number	Visit 01	Visit 02	Visit 03	Visit 04
Study Timelines	D0	D7	D56+7	Post-RSV season*
Time Windows (Days)				
Vaccination	X			
Blood Samples (mL)	5†	-	5	5*
Total volume of blood collected (mL)	5	-	5	5

† All participants screened will provide a blood sample up to 5 mL at enrollment (Visit 01) prior to receipt of the first administration of assigned study product, for baseline RSV serum antibody testing.

* All participants will provide a blood sample up to 5 mL during the month following the RSV season or at least five months after the last vaccine administration for the measurement of post-season RSV antibody titers, respectively, to determine if a 4-fold or greater rise in RSV antibody titers has occurred during the RSV season.

Table 5-2: Schedule of blood sample collection (volume in mL) – Cohorts 2 and 4

Visit Number	Visit 01	Visit 02	Visit 03	Visit 04	Visit 05	Visit 06
Study Timelines	D0	D7	D56+7	D63+7	D84+8	Post-RSV season‡
Time Windows (Days)						
Vaccination	X		X			
Blood samples (mL)	5†	-	5*	-	5*	5‡
Total volume of blood collected (mL)	5	-	5	-	5	5

† All participants screened will provide a blood sample up to 5 mL at enrollment (Visit 01) prior to receipt of the first administration of assigned study product, for baseline RSV serum antibody testing.

* All the participants will provide a blood sample up to 5 mL at the D56 Visit (before vaccination 2), and then at D84 Visit for the measurement of post-vaccination serum antibodies to RSV.

‡ All participants will provide a blood sample up to 5 mL during the month following the RSV season or at least five months after the last vaccine administration for the measurement of post-season RSV antibody titers, to determine if a 4-fold or greater rise in RSV antibody titers has occurred during the RSV season.

5.1.4 Visit Procedures

See Table of Study Procedures for Cohorts 1, 2, 3 and 4.

5.1.4.1 In-Person Visits

Visit 01 (Day 0) for Cohorts 1, 2, 3 and 4

Timelines for the end of enrollment (Visit 01), vaccination and RSV surveillance per hemisphere are shown in [Table 5-3](#).

Table 5-3: Timelines for end of enrollment and vaccination per hemisphere

	Infants and Toddlers 6 to 18 Months of Age			
	Northern Hemisphere (USA) Cohort 1 (1 administration)	Southern Hemisphere (Latin America) Cohort 2 (2 administrations)	Northern Hemisphere (USA) Cohort 3 (1 administration)	Northern and Southern Hemispheres (USA and Latin America) Cohort 4 (2 administrations)
Earliest day for enrollment (Visit 01)	01 August 2020	01 November 2020	01 April 2021	USA - 01 June 2021 Canada – May 2022 Chile - November 2021 Honduras - April 2022 South Africa - June 2022
Last day for enrollment (Visit 01)	5 days before the start of the RSV season	61 days before the start of the RSV season	31 May 2021	Not applicable
Last day for Visit 03 (D56) Vaccination 2	-	5 days before the start of the RSV season	-	Not applicable

Visit 01 (Day 0): Enrollment, Randomization, and Vaccination Procedures for Cohorts 1, 2, 3 and 4 (All Participants)

- 1) Give the participant's parent / guardian / legally authorized representative information about the study, obtain written informed consent, and give him / her a signed copy.
- 2) Collect demographic data (including date of birth, sex, race, and ethnicity).
- 3) Check inclusion and exclusion criteria for eligibility.
- 4) Obtain verbal medical history about the participant, including past and ongoing medication, any signs and symptoms, and developmental delays.
- 5) Review any past medical records including the immunization record to ensure participant will not meet exclusion criteria 2, 3 and 21.
- 6) Prior to randomization conduct a full physical examination including body temperature, heart rate, respiratory rate, weight, length and assessment of HEENT [head, ears, eyes, nose, and throat], lungs, heart, and abdomen, musculoskeletal, age-appropriate neurological and skin exam.
- 7) Perform Coronavirus Disease 2019 (COVID-19) point of care diagnostic test (POC).
- 8) Contact the IRT for participant number, randomization and dose number based on age subgroup. Additional information regarding randomization is in the Operating Guidelines.
- 9) Obtain the first blood sample, to test the baseline RSV antibody serostatus, i.e., serum RSV-nAb titer ([Section 7.1](#) for detailed instructions regarding the handling of blood samples and Operating Guidelines for further details).
- 10) Administer the appropriate study product, follow the instructions provided for the intranasal administration of study vaccine using the [REDACTED] in the Study Operating Guideline.
- 11) Keep the participant under observation for 30 minutes and record any adverse reaction in the source document.
- 12) Give or download the parent / guardian / legally authorized representative a diary card (DC1) / eDC and a thermometer and go over the instructions for their use, as detailed in the Study Operating Guideline, and remind to complete the Day 0–7 pages of DC1 / eDC. The parent / guardian / legally acceptable representative will record the child's temperature and signs of illness (solicited reactions and unsolicited AEs, including AESIs, MAAEs and SAEs) on the DC1 / eDC.
- 13) Remind the parent / guardian / legally authorized representative to expect a telephone call from the study site nurse daily after this immunization Visit 01 to review what they have entered daily in the DC1 / eDC; and to complete the remaining entries of DC1 / eDC and bring to Visit 02 at the specified date.
- 14) Remind the parent / guardian / legally authorized representative to notify the site in case of an SAE or any illness. The site staff, upon evaluation, will schedule an Illness Visit within the stipulated time frame of site notification, if required.
- 15) Complete the relevant case report forms (CRFs) for this visit.

Visit 02: Day 07 Post-Vaccination 1 Visit Procedures for Cohorts 1, 2, 3 and 4 (All Participants)

- 1) Review medical history, including past and ongoing medication since the last visit.
- 2) Perform a focused clinical examination including temperature, pulse, and respirations, ears, eyes, nose, throat (EENT), respiratory, cardiac and lymphatic system.
- 3) Obtain a nasal swab sample for viral quantification of vaccine virus shedding. If the participant meets criteria for an Illness Visit at Day 7, the same nasal swab specimens may also be tested for respiratory pathogens.
- 4) Review the solicited reactions and unsolicited AEs, AESIs, MAAEs and SAEs in the completed DC1 / eDC with the participant's parent / guardian / legally authorized representative. Provide instruction to complete DC2.
- 5) If an SAE occurred, follow the instructions in [Section 10](#) for reporting it. Remind to notify the site in case of an SAE.
- 6) Complete the relevant CRFs for this visit.
- 7) Remind the parent / guardian / legally acceptable representative of the following visit.

Visit 03: Day 56+7 Post-Vaccination 1 Visit Procedures for Cohort 1 and 3

- 1) Review medical history, including past and ongoing medication since the last visit. Check for contraindications.
- 2) Perform a focused clinical examination including temperature, pulse, and respirations, EENT, respiratory, cardiac and lymphatic system.
- 3) Obtain a blood sample for serum antibodies to RSV (see [Section 7.1](#) for detailed instructions regarding the handling of blood samples).
- 4) Collect and review SAEs in the completed DC1 and DC2 / eDC with the participant's parent / guardian / legally authorized representative. Provide MA.
- 5) If an SAE had occurred, follow the instructions in [Section 10](#) for reporting it. Remind to notify the site in case of an SAE.
- 6) Complete the relevant CRFs for this visit.
- 7) Remind the parent / guardian / legally authorized representative of the following visit.

Visit 03: Day 56+7 Post-Vaccination 1 Visit Procedures for Cohorts 2 and 4

- 1) Obtain verbal medical history about the participant, including past and ongoing medication and immunizations.
- 2) Check for contraindications for receipt of second vaccination.
- 3) Prior to vaccination, conduct a focused clinical examination including temperature, pulse, and respirations, EENT, respiratory, cardiac and lymphatic system.
- 4) Perform COVID-19 POC diagnostic test.
- 5) Collect reportable concomitant medications / vaccinations.

- 6) Contact the IRT for dose number.
- 7) Obtain a blood sample for serum antibodies to RSV (see [Section 7.1](#) for detailed instructions regarding the handling of blood samples).
- 8) Administer the appropriate study product, follow the instructions provided for the intranasal administration of study vaccine using the [REDACTED] in the Study Operating Guideline.
- 9) Keep the participant under observation for 30 minutes and record any adverse reaction in the source document.
- 10) Collect and review solicited reactions and unsolicited AEs, including AESIs, MAAEs and SAEs in the completed DC1 and DC2 / eDC with the participant's parent / guardian / legally authorized representative.
- 11) Give or download the parent / guardian / legally authorized representative a diary card (DC3) / eDC and a thermometer and go over the instructions for their use, as detailed in the Study Operating Guideline, and remind to complete the Day 0–7 pages of DC3 / eDC. The parent / guardian / legally authorized representative will record the child's temperature and signs of illness (solicited reactions and unsolicited AEs, including AESIs, MAAEs and SAEs) on the DC3 / eDC.
- 12) Remind the parent / guardian / legally authorized representative to expect a telephone call from the study site nurse daily after this Visit 04 to review what they have entered daily in the DC3 / eDC, and to complete the entries of DC3 and bring to Visit 05 at the specified date and time.
- 13) Remind the parent / guardian / legally authorized representative to notify the site in case of an SAE or any illness. The site staff, upon evaluation, will schedule an Illness Visit within the stipulated time frame of site notification, if required.
- 14) Complete the relevant CRFs for this visit.

Post-RSV Season or ≥ 5 Months After Last Vaccine Administration Visit for All Cohorts (Visit 04 for Cohorts 1 and 3 or Visit 06 for Cohorts 2 and 4)

- 1) Obtain a blood sample for serum antibodies to RSV.
- 2) Review the MA for SAEs with the participant's parent / guardian / legally authorized representative.
- 3) If an SAE had occurred, follow the instructions in [Section 10](#) for reporting it. Remind to notify the site in case of an SAE.
- 4) Complete the relevant CRFs for this visit and the End of Study CRF.

Visit 04: D63+7 Post-Vaccination 1 (Day 07 Post-Vaccination 2) Visit Procedures for Cohorts 2 and 4

- 1) Review medical history, including past and ongoing medication since the last visit.
- 2) Perform a focused clinical examination including temperature, pulse, and respirations, EENT, respiratory, cardiac and lymphatic system.

- 3) Obtain a nasal swab sample for quantification of vaccine virus shedding. If the participant meets criteria for an Illness Visit, the same nasal swab specimens may also be tested for respiratory pathogens.
- 4) Review the solicited reactions and unsolicited AEs, AESIs, MAAEs and SAEs in the completed DC3 / eDC with the participant's parent / guardian / legally authorized representative.
- 5) If an SAE occurred, follow the instructions in [Section 10](#) for reporting it. Remind to notify the site in case of an SAE.
- 6) Complete the relevant CRFs for this visit.

Visit 05: D84+8 Post-Vaccination 1 (Day 28+8 Post-Vaccination 2) Visit Procedures for Cohorts 2 and 4

- 1) Review medical history, including past and ongoing medication and immunizations since the last visit.
- 2) Perform a focused clinical examination including temperature, pulse, and respirations, EENT, respiratory, cardiac and lymphatic system.
- 3) Obtain a blood sample for serum antibodies to RSV.
- 4) Collect and review the solicited reactions and unsolicited AEs, AESIs, MAAEs and SAEs in the completed DC3 / eDC with the participant's parent / guardian / legally authorized representative. Provide MA.
- 5) If an SAE had occurred, follow the instructions in [Section 10](#) for reporting it. Remind to notify the site in case of an SAE.
- 6) Complete the relevant CRFs for this visit.

Visit 99: Illness Visits

Illness visits can be conducted remotely, as a home visit or an onsite visit depending on the judgment of the investigator. The requirement for an Illness Visit and which type of illness visit will be evaluated first by video call. The video call will be used to initially remotely evaluate the study participant's clinical status and whether the illness can be managed remotely especially for mild (Grade 1) illness. This staged management of illness visits is required during the current COVID-19 pandemic situation to limit the number of contacts between the study participant and study site staff to only those that are absolutely required. Guidelines for remote evaluation are described in the Operating Guidelines.

The timeframe after site notification in which the Illness Visit must occur, if deemed necessary by the Investigator, depends on grading of the fever and respiratory symptoms and the phase of the study. If the Illness Visit occurs on a day concurrent with a routine Study Visit when a nasal swab specimen is to be collected, the same nasal swab specimen would be used to test for respiratory pathogens. A second nasal swab should be collected 48 hours later. If the Illness Visits occurs on a day concurrent with a routine Study Visit when a nasal swab specimen is not collected, a nasal

swab specimen is required to test for respiratory pathogens. A second nasal swab should be collected 48 hours.

If illnesses/safety events occur, the study participant should be managed according to the site/local standard of care, including the conduct of lab investigations required for diagnosis and/or management of the study participant. Following an Illness Visit, medical personnel should continue to follow participants until resolution.

Illness visits may occur at any time during the study. The Illness visit timeframes are summarized in [Table 5-4](#).

Table 5-4: Illness visit timeframe

Phase	Symptom	Grade	Visit timeframe
Acute (post-vaccination to midnight 28 days after each vaccination)*	Fever, acute otitis media or URI	1	Within 3 days
		> 1	Within 2 days
	LRI	Any	Within 2 days
	SAEs	Any	Within 2 days
Post-acute (12:01am on 29 th day after post-vaccination to midnight 56 days after each vaccination)*	SAEs	Any	Within 2 days
RSV surveillance season (on average, 01 November to 31 March for NH and 01 May to 30 September for SH)*	Medically attended fever, acute otitis media, URI or LRI	>2	Within 3 days
	SAEs	Any	Within 2 days
Post-RSV season (on average, 01 to 31 April for NH and 01 to 31 October for SH) or at least 5 months after last vaccine administration	SAEs	Any	Within 2 days

LRI, lower respiratory tract illness; NH, Northern hemisphere; RSV, Respiratory Syncytial Virus; SAE, serious adverse event; SH, Southern hemisphere; URI, upper respiratory tract illness

*In some circumstances, acute phase or post-acute phase may overlap with the RSV surveillance season, in which case the more conservative visit timeframe should be considered.

Illness Visit procedures are as follows:

- 1) Obtain verbal medical history about the participant, including past and ongoing medication and immunizations.
- 2) Determine whether the participant can be managed remotely or if an at home visit or an onsite illness visit is required.
- 3) If an at home or onsite visit, perform a focused clinical examination including temperature, pulse, and respirations, EENT, respiratory, cardiac and lymphatic system. Instructions for

conducting a focused clinical examination remotely are described in the Operating Guidelines.

- 4) Collect and review the solicited and unsolicited AEs, AESIs, MAAEs and SAEs in the completed DC / eDC or memory aid with the participant's parent / guardian / legally authorized representative.
- 5) If an SAE had occurred, follow the instructions in **Section 10** for reporting it. Remember to notify the site in case of an SAE, if illness starts within the 28 days of vaccination.
- 6) Obtain a nasal swab sample for RSV viral detection and [REDACTED] for respiratory pathogens.
- 7) COVID-19 testing if required according to the opinion of the investigator and CDC COVID testing algorithm.^a
- 8) Complete the relevant CRFs for this visit.
- 9) Schedule follow-up as appropriate, including a visit for the collection of a confirmation nasal swab 48 hour later.
- 10) If illnesses/safety events occur, the participant should be managed according to the site/local standard of care, including the conduct of lab investigations required for diagnosis and/or management of the study participant.

Specific guidance for illness visits, including use of personal protective equipment (PPE) for full contact and droplet precaution, are described in the Operating Guidelines.

Follow-up of participants with solicited reactions or with AEs That Led to Study/Vaccination Discontinuation:

Unless a participant or participant's parent / guardian / legally authorized representative refuses further contact, each participant who experiences an AE (whether serious or non-serious) during the study must be followed until the condition resolves, becomes stable, or becomes chronic (even after the end of the participant's participation in the study) if either of the following is true:

1. The AE is considered by the Investigator to be related to the product administered.
2. The AE caused the discontinuation of the participant from the study or from vaccination.

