1:1 randomized, placebo-controlled, 1 dose of RSV Δ NS2/ Δ 1313/I1314L [REDACTED], 2 administrations ([REDACTED] in total per administration) at D0 and D56, n=20 per vaccine group. Participant enrollment will be initiated at approximately 4 sites in Latin America ((Argentina and Chile) at the earliest in November/December 2020. The first and the second vaccine administrations (D0 and D56, respectively) will be completed at least 5 days before the beginning

of the RSV season (the average 5-month RSV season in the southern hemisphere is 01 May to 30 September).

Cohort 3 (Northern Hemisphere):

1:1 randomized, placebo-controlled, 1 dose of RSV ΔNS2/Δ1313/I1314L [REDACTED] [REDACTED]
1 administration ([REDACTED] per administration in total) at D0, n=20 per vaccine group. Participant enrollment will be initiated at approximately 30 sites in the US in April 2021. Vaccine administrations will be completed before 31 May 2021. If recruitment in Cohort 3 does not reach the goal of n=40, no attempt will be made to include more participants receiving 1 administration in Cohort 4.

Cohort 4 (Northern and Southern Hemisphere):

1:1:1 randomized, placebo-controlled, 2 doses of RSV ΔNS2/Δ1313/I1314L ([REDACTED]
[REDACTED]), 2 administrations ([REDACTED] per administration in total) at D0 and D56, n=60 per vaccine group. Participant enrollment will be initiated at approximately 30 sites in the US at the earliest in June 2021, approximately 2 sites in Canada at the earliest in May 2022, approximately 2 sites in Chile at the earliest in November 2021, approximately 2 sites in Honduras at the earliest in April 2022, and approximately 2 sites in South Africa at the earliest in June 2022.

The first and the second vaccine administrations will be completed at any time of the year, including the winter RSV season, regardless if normal RSV seasonality is restored after the disruption due to COVID-19 non-pharmaceutical interventions.

Blood Sampling:

All participants screened for inclusion in Cohorts 1, 2, 3 and 4 will provide a blood sample at enrollment (Visit 01), for baseline RSV serum antibody testing.

All participants in each vaccine group in Cohorts 1, 2, 3 and 4 will provide a blood sample at the D56 Visit (before vaccination 2 for Cohorts 2 and 4), for the measurement of post-vaccination serum antibody titers to RSV.

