5.1.2 Justification of the Study Design

For this Sanofi Phase I/II trial, data will be analyzed according to serostatus. Baseline serostatus will be retrospectively determined from serum samples collected at baseline. Participants will be categorized into RSV-experienced or RSV-naïve based on the presence or absence of detectable serum RSV anti-F IgA antibodies. This biomarker has been chosen since it is produced only in response to RSV infection and not transferred trans-placentally from mother to child.

Evaluation of post-vaccination immunogenicity on Day 56 for Cohorts 1, 2, 3 and 4 and Day 84 for Cohorts 2 and 4:

To date, all studies with live-attenuated RSV candidate vaccines have used Day 56 as the time point to assess serum antibody response post-vaccination with a single dose administration. This time point is used for two reasons: 1) since this is a primary response (rather than an anamnestic [memory] response), serum antibody response may not have reached maximal levels by Day 28 and 2) maximal replication of these highly attenuated vaccine viruses does not typically occur until Day 7, which may also delay induction of the immune response. In participants receiving 2 administrations of vaccine, this is no longer likely to be a primary response and rather an anamnestic (memory) response and serum antibody response is likely to be maximal by Day 28 after the second vaccination.

RSV season or post-vaccination RSV surveillance for Cohort 4:

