5.2.8 Conditions for Withdrawal

Parents / guardians / legally authorized representatives will be informed that they have the right to withdraw their child from the study at any time. Any participant who has received study product will be encouraged to remain in study follow-up for the duration of the study even if sample collection is refused.

A participant may be withdrawn from the study:

- At the request of the parent / guardian / legally authorized representative either verbally or in writing (i.e., withdrawal of consent/dropout).
- At the discretion of the Investigator or Sponsor due to safety concern of significant non-compliance with the protocol (based on the Investigator's judgment), without the parent's / guardian's / legally authorized representative's permission (i.e., non-compliant with the protocol/withdrawal).

The reason for a withdrawal or dropout should be clearly documented in the source documents and in the CRB.

The Investigator must determine whether voluntary withdrawal is due to safety concerns (in which case, the reason for discontinuation will be noted as “Adverse Event”) or for another reason.

Withdrawn participants will not be replaced.

For any participant who withdraws or is terminated from the study prior to scheduled completion of follow-up, study staff will document the reason for the withdrawal or termination in detail and will make every effort to complete the following final evaluations:

- 1) Obtain verbal medical history about the participant, including past and ongoing medication and immunizations.
- 2) Obtain a blood sample for serum antibodies to RSV if possible (see [Section 7.1](#) for detailed instructions regarding the handling of blood samples).
- 3) Obtain a nasal swab sample for quantification of vaccine virus shedding (if in the Acute Phase), other respiratory pathogens including a COVID-19 POC test on the discretion of the investigator.
- 4) Complete the relevant section of the CRF.

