12.2.3 Per-Protocol Analysis Set

The per-protocol analysis set (PPAS) is a subset of the FAS. Two specific PPAS will be defined: PPAS1 after 1 administration (for participants in Cohorts 1, 2, 3 and 4) and PPAS2 after 2 administrations (for participants in Cohorts 2 and 4).

The participants presenting with at least one of the following relevant protocol deviations will be excluded from the PPAS:

- Baseline serology blood sample was not collected at visit 01 (D0).

- Participant with temporary contraindication did not receive vaccination 1 in the proper time window from randomization.
- Participant did not meet all protocol-specified inclusion criteria or met at least one of the protocol-specified exclusion criteria
- Participant did not receive vaccine / did not complete the vaccination schedule
- Participant received a vaccine other than the one that he / she was randomized
- Preparation and / or administration of vaccine not done as per-protocol
- Participant received a protocol-prohibited therapy before the post-vaccination serology blood sample (see [Section 6.7.1](#))
- Participant with confirmed diagnosis of wt RSV before the post-vaccination serology blood sample
- Participant with an emergency unblinding performed by the Investigator

The participants presenting with at least one of the following relevant protocol deviations will be excluded from the PPAS1 only:

- Post-vaccination 1 serology blood sample not collected at visit 03
- Post-vaccination 1 serology blood sample not collected at visit 03 in the proper time window

The participants presenting with at least one of the following relevant protocol deviations will be excluded from the PPAS2 only (for participants in Cohorts 2 and 4):

- Participant did not receive vaccination 2 at visit 03 in the proper time window
- Post-vaccination 2 serology blood sample not collected at visit 05
- Post-vaccination 2 serology blood sample not collected at visit 05 in the proper time window

In addition to the reasons listed above, participants will also be excluded from the PPAS if their baseline serology sample or their post-vaccination serology sample did not produce a valid test result (i.e., result for RSV A serum neutralizing antibody titers is missing).

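### Visit 01 randomises the child before the baseline blood draw, and the protocol gives no rule for a failed draw, so an allocated child can be lost to the RSV-naive primary immunogenicity analysis

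*Protocol*

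**What the plan says.** Protocol 5.1.4.1 lists the Visit 01 procedures by number. Step 6, the physical examination, is expressly placed before randomisation. Step 8 is "Contact the IRT for participant number, randomization and dose number based on age subgroup". Step 9 is "Obtain the first blood sample, to test the baseline RSV antibody serostatus, i.e., serum RSV-nAb titer". Step 10 gives the product.

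On the timing of the sample, the footnotes to Tables 5-1 and 5-2 (5.1.3) say "All participants screened will provide a blood sample up to 5 mL at enrollment (Visit 01) prior to receipt of the first administration". Section 5.1.1 says "All participants screened for inclusion in Cohorts 1, 2, 3 and 4 will provide a blood sample at enrollment (Visit 01"), for baseline antibody testing. Both tie the sample to enrolment and the first of them to dosing. Neither says it must be in hand before randomisation.

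On its use, 5.1.2 says "Baseline serostatus will be retrospectively determined from serum samples collected at baseline". SAP 4.4.2.3 classes a child with a missing or not-reportable baseline IgA as Undetermined. Protocol 9.1.3.2 limits the primary immunogenicity endpoint to RSV-naive participants. SAP 4.4.2.2 makes a fold-rise missing when either titer is missing, and Protocol 12.3.2 and SAP 5.3.2 rule out imputation. The first per-protocol exclusion in 12.2.3 is "Baseline serology blood sample was not collected at visit 01 (D0").

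On replacement, 5.2.8 says "Withdrawn participants will not be replaced".

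**The concern.** The baseline sample cannot be recovered once the product is given, and the primary immunogenicity objective cannot use a child who lacks it. The protocol could have made the draw a condition of allocation, as it does for the physical examination, but places it after the IRT call. Having a baseline sample is not among the inclusion or exclusion criteria (5.2.4, 5.2.5). The postponement allowed after randomisation (5.2.7.1) covers listed illnesses and recent vaccines or investigational drugs, not a failed venipuncture.

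In infants from 6 months of age, with up to 5 mL to be drawn, some failed draws are foreseeable. When one happens the allocation has already been used. At stake is a loss after randomisation that could instead fall before it, in a trial whose cohort arms have as few as 20 children.

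**Working it through.** **Plan's own figures (Protocol 12.5, SAP 5.5).** The probability of seeing at least one event is 1 − (1 − p)^n.
- Low-dose: 1 − 0.97^100 = 0.952, stated as 95%.
- High-dose: 1 − 0.9625^80 = 0.953, stated as 95%.
- Table 12-1 is N × rate and N × (1 − rate). Every cell reproduces; for example, the high-dose RSV-naive count runs from 80 × 0.95 = 76 down to 80 × 0.65 = 52.

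None of these figures allows for missing baseline samples.

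**What follows from a missing baseline.**

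| Analysis | Child dosed | Child not dosed |
|---|---|---|
| RSV-naive primary immunogenicity | lost (serostatus Undetermined) | lost |
| GMTR and seroresponse | lost (fold-rise missing) | lost |
| Shedding and infectivity by serostatus | lost | lost |
| PPAS1 and PPAS2 | excluded | excluded |
| FAS | kept (12.2.1) | not in set |
| SafAS and primary safety | kept (12.2.2) | not in set |

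**Children affected.** Let f be the proportion of failed draws. The documents give no value, so f = 2-5% is an assumption.
- Whole trial: 0.02 × 300 = 6 to 0.05 × 300 = 15.
- Cohort 4 arm: 0.02 × 60 = 1.2 to 0.05 × 60 = 3.
- Cohort 1-3 arm: 0.02 × 20 = 0.4 to 0.05 × 20 = 1.
- RSV-naive children, high-dose group: 0.02 × 52 = 1.0 to 0.05 × 76 = 3.8.
- Chance of at least one such child, 1 − (1 − f)^n: 33% to 64% in an arm of 20, and 70% to 95% in an arm of 60.

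**Effect on precision.** Evaluable RSV-naive children = N × (1 − f) × (1 − experienced rate). I took 20% RSV-experienced (within the Table 12-1 range) and 80% seroresponse (the 16 of 20 in Protocol 1.1), rounded counts to whole children, and used the Clopper-Pearson interval. The comparison is f = 0 against a deliberately high f = 10%.

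| Group | RSV-naive n | 95% CI half-width (points) |
|---|---|---|
| Low-dose, N = 100 | 80 → 72 | 9.3 → 9.7 |
| High-dose, N = 80 | 64 → 58 | 10.5 → 11.1 |
| One arm of 20 | 16 → 14 | 20.8 → 23.1 |

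The cost is 0.4 to 0.6 points in the pooled dose groups and about 2 points in a 20-child arm. The last row matters because SAP 5.1 plans analyses by cohort as well as pooled.

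**The case against.** The sample already has to precede dosing. A failed draw can therefore be noticed before step 10, and dosing without it would depart from the footnotes in 5.1.3. Inclusion criterion 3 expects the family to be able to comply with all procedures. Steps 8 and 9 refer to the Operating Guidelines, which are not among the documents and may hold a failed-draw rule. All of this stands. It narrows the point to an unstated rule and an avoidable order of steps; it does not remove it, because the allocation has been made by the time the draw is tried.

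A reader might infer that such children bias the comparison between arms. The documents do not support that. The draw comes before any product is given, parents and safety assessors are blinded (6.4), and nothing suggests that venipuncture would fail more often in one arm.

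A reader might also infer that these children contribute nothing, or that the protocol forbids replacing them. A dosed child still counts for primary safety, which is assessed regardless of serostatus, and for the FAS. The sentence in 5.2.8 covers withdrawn participants, and a dosed child who stays in follow-up is not withdrawn. What can be said is that no section provides for a replacement, and that 5.1.1 declines to make up recruitment shortfalls in Cohorts 1 and 3 through the next cohort.

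Finally, simply exchanging steps 8 and 9 would not work. Section 7.1 has staff check the assigned participant number on the tube label immediately before the draw, and that number comes from the IRT (6.5). This objection is decisive against a plain swap and shapes the fix.

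**Conclusion.** The point holds as a modest design improvement. Visit 01 allocates the child before securing the one sample on which the RSV-naive primary analysis depends, and the protocol and SAP are silent on a failed draw. The expected cost is a small loss of precision, probably non-differential: 6-15 of 300 children, including about 1-4 RSV-naive children in the high-dose group, if 2-5% of draws fail. That rate is an assumption. The trial is descriptive (12.1.1.1), so no powered figure changes, and the loss is small beside the 52-76 range that Table 12-1 already accepts. The conclusion would weaken further if the Operating Guidelines contain a rule.

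A separate wording conflict is certain. Step 9 identifies serostatus with the neutralizing titer, whereas Protocol 5.1.2, 9.1.3.1 and SAP 4.4.2.3 define it by serum IgA.

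**What to change.** Split step 8 of Visit 01 into two IRT transactions:
1. The IRT assigns the participant number, so that the tube can be labelled and checked as 7.1 requires.
2. The baseline sample is drawn.
3. The site confirms in the IRT that the sample was obtained, and only then does the IRT release the randomisation and dose number.

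A child whose draw fails is rescheduled or not randomised. The Table of Study Procedures already lists number allocation and randomisation as separate rows, so the split fits the existing structure. If the sponsor prefers the present order, the protocol should at least state how a failed draw affects the allocation, administration of product and each analysis set.

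Reconcile step 9 with 9.1.3.1 and SAP 4.4.2.3 by naming serum anti-F IgA for serostatus and the RSV A neutralizing titer as the baseline for fold-rise.

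The cost is a two-stage IRT transaction with one confirmation field, and a few children rescheduled or not enrolled. No procedure is added. The change does not help when the serum is insufficient or the IgA result is not reportable, because IgA is tested retrospectively; those children would still be Undetermined after randomisation.
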